### Data analysis

Effectiveness analysis will be on the individual level. Due to the high degree of homogeneity (in income and race) among the eligible schools, focus will be placed on detecting potential selection bias on the individual level program participation and attrition. Appropriate descriptive, parametric, and non-parametric statistical methods will be used to compare continuous and categorical variables among the intervention conditions at baseline. Data will be examined for the presence of outliers, violations of normality for continuous variables, and missing data. Major violations of normality will be corrected with an appropriate transformation procedure. All analysis will use cluster-robust standard error adjustment.

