### Power calculation and sample size

Given the lack of interventions and designs similar to Kids SIPsmartER, data from the Kids SIPsmartER feasibility study were used to estimate the effect size and intraclass correlation (ICC) of students' SSB intake. Considering the school size eligibility criteria and anticipated variation in the number of students per school (range 80-200 students, average 133 students), a lower and upper range of power is estimated. Due to the cluster-randomized block design (i.e., randomization at school level), no attrition at the school level is anticipated. The sample size calculations are conservatively based on a small 7-month effect size of 0.3, a 0.05 type I error, and a 0.01 ICC of students' SSB intake. To achieve 80% power under these assumptions, a total of 12 schools/clusters (6 schools per condition) are needed, with 54 enrolled students per school (and 49 retained after an anticipated 10% attrition rate at student level at 7-month). Following these same assumptions, 99.99% power would be achieved with a total of 12 schools/clusters and an average of ~115 students enrolled per school (and 104 retained after an anticipated 10% attrition rate). In sum, using conservative effect size and ICC estimates and standard type I error rate, enrolling a minimum of 54 students and up to 115 students per 12 schools/clusters would provide adequate power ranging from 80% to 99.9% for the primary 7-month SSB student outcome.

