#### ***Primary effectiveness aim***

Multi-level mixed effect models will be used to control errors of non-independence and heteroscedasticity caused by individual, class and school heterogeneity, and potential covariates identified a priori based on the literature and theory that are relevant to SSB behavior changes. The treatment effect models used in this study will contain outcomes of interest as dependent variables (e.g., SSB kcal, quality of life measures etc.). Specific mixed effect link function will be chosen to fit different outcome distributions. The models will control those unobserved effects that are fixed over time at three different levels (i.e., individual student, class, and school) and

those unobserved time and block fixed effects that are individual-class-school-invariant. To further examine intervention treatment effect differences across blocks, we will modify the models to allow group indicator to interact with time-block fixed effects.

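### With 12 randomised schools, the SAP's cluster-robust standard errors come with no required small-sample correction or df, and the ordinary versions do not hold the 5% level

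*SAP*

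**What the plan says.** The SAP's Data analysis section ends with the rule "All analysis will use cluster-robust standard error adjustment". It gives no clustering level, estimator, reference distribution or df, and no other section supplies them.

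The Power section says "a total of 12 schools/clusters (6 schools per condition) are needed" and bases the design on "a small 7-month effect size of 0.3, a 0.05 type I error", without saying whether the test is one- or two-sided. It describes schools as "range 80-200 students, average 133 students". The Protocol's Study Logistics section randomises the schools in three blocks of four, two to each condition.

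Under Primary effectiveness aim, the SAP specifies multilevel mixed models for "heteroscedasticity caused by individual, class and school heterogeneity". These models control for "those unobserved time and block fixed effects that are individual-class-school-invariant". To study how the effect varies between blocks, they are later changed to "allow group indicator to interact with time-block fixed effects".

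**The concern.** The sandwich variance relies on many clusters. With 12, the school-level residuals are shrunk by every parameter the model fits to the school means, so the ordinary estimator is too small on average. A normal reference also ignores how imprecise that estimator is. The result is p-values that are too small and intervals that are too narrow.

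A low ICC does not help, because the bias comes from the number of schools. Nor does the mixed model remove it, since the robust adjustment is applied on top and therefore determines the p-value. At stake are the 0.05 level of the primary 7-month comparison and the linear secondary outcomes tested with the same contrast. Because the method is left open, it could also be chosen after the data are seen.

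**Working it through.** **Inputs.** From the SAP Power section: 12 schools, 6 per condition; alpha 0.05; effect 0.3, taken as standardised; ICC 0.01; 49 or 104 students retained per school; school sizes 80-200, mean 133; 10% attrition. From the Protocol: three blocks of four schools (Study Logistics) and 86% consent (Participant Groups, Students). Assumptions: two-sided test, linear outcome, clustering on school.

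**1. The plan's own power figures.** For a 7-month comparison of school means with m students each, SE = sqrt(2 × (1 + (m-1) × 0.01) / (6m)).
- m = 49: SE = sqrt(2 × 1.48 / 294) = 0.1003, so 0.3/SE = 2.99.
- m = 104: SE = sqrt(2 × 2.03 / 624) = 0.0807, so 0.3/SE = 3.72.

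| Reference | m = 49 | m = 104 |
|---|---|---|
| Stated in SAP | 80% | 99.99% |
| Normal | 84.8% | 96.1% |
| t, 10 df | 76.9% | 91.7% |
| t, 8 df | 74.5% | 90.1% |

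No row reproduces both stated figures.

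**2. School-level df.** Without block terms on the tested contrast, df = 12 - 2 = 10. This includes a baseline-to-7-month model with block main effects, because those cancel from the change. With block-by-time terms, or block terms on 7-month values or change scores, df = 12 - 4 = 8.

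**3. Size with balanced schools.** The plain sandwich SE equals the unbiased SE × sqrt(df/12). G/(G-1) scaling multiplies it by sqrt(12/11). With c the critical value (1.960 for normal, 2.201 for t on 11 df) and f the combined factor, size = 2 × P(t_df > c × f), and relative interval width = c × f / t_df(0.975). The correct t values are 2.228 (10 df) and 2.306 (8 df).

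| Estimator, reference | 10 df: c × f | Size | Width | 8 df: c × f | Size | Width |
|---|---|---|---|---|---|---|
| Plain, normal | 1.960 × 0.913 = 1.789 | 10.4% | 80% | 1.960 × 0.816 = 1.600 | 14.8% | 69% |
| G/(G-1), normal | 1.960 × 0.953 = 1.869 | 9.1% | 84% | 1.960 × 0.853 = 1.672 | 13.3% | 72% |
| Plain, t11 | 2.201 × 0.913 = 2.009 | 7.2% | 90% | 2.201 × 0.816 = 1.797 | 11.0% | 78% |
| G/(G-1), t11 | 2.201 × 0.953 = 2.099 | 6.2% | 94% | 2.201 × 0.853 = 1.877 | 9.7% | 81% |

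A simulated two-wave model with block main effects agrees with the 10 df column, in the same row order: 10.2%, 8.9%, 7.1% and 6.2%.

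**4. Size with unequal schools.** The SAP gives only the range and mean, so these sizes are assumed: 80, 80, 90, 100, 110, 120, 130, 145, 160, 181, 200, 200 (mean 133). Multiplying by 0.86 and 0.90 leaves 62-155 students per school. Twelve school-mean changes were simulated with variance ICC + (1 - ICC)/n, ICC of change 0.01 or 0.03, and 20,000 null runs each. With weights proportional to n and no block terms, size is 11.4-11.6% (plain, normal), 10.1-10.4% (G/(G-1), normal) and 7.1-7.2% (G/(G-1), t11). With weights that allow a random school effect on change, results stay close to the balanced table.

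**5. A corrected method.** CR2 with t on the school-level df gives exactly 5.0% in the balanced closed form. With Satterthwaite df and unequal schools it gives 4.7-5.5% in simulation.

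**The case against.** The strongest reply is that the SAP leaves the estimator unspecified rather than choosing a wrong one. Its sentence is compatible with CR2, and the documents name no software. This stands: every rate above is conditional on an ordinary sandwich being used. The mildest option, at 6.2% with 94% of the correct width, is a small departure on 10 df. But the sentence does not require a correction, and all four ordinary options exceed 5%.

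The clustering level is also less open than the sentence suggests. The Protocol and the Power section both call schools the clusters. A reader might infer from the class level in the model that errors will be clustered on class, with further inflation. The documents do not support a figure for that, since they give neither the number of classes nor a class ICC.

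The choice between 10 and 8 df cannot be settled from the text. Time-block effects may enter only in the extension, or may already be in the base model with only the group interaction new. Nor is school weighting stated. Effects fixed over time imply something near n-weights for the change, so the balanced range should not be read as covering every model.

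Finally, the power recalculation concerns a 7-month comparison. For a baseline-to-7-month contrast it would be the same only at a within-student correlation of 0.5. Assumed correlations of 0.3-0.7 give roughly 63-93% with 49 per school on 10 df.

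**Conclusion.** The concern holds in conditional form. With 12 schools, an ordinary school-clustered sandwich gives a true two-sided size of about 6-10% (balanced, 10 df), 7-12% (unequal assumed sizes weighted by n, no block terms) or 10-15% (balanced, 8 df), against the nominal 5%. This assumes a linear outcome. Size was not computed for non-linear outcomes, the structural equation models or the within-school delivery comparison.

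Two stronger readings are not supported. A reader might infer that the primary test will be anticonservative; the SAP does not fix the estimator, so it may not be. A reader might also attribute the whole gap between the SAP's "99.99% power would be achieved with a total of 12 schools/clusters" and the recalculated 90-92% to the df. Part of it is a separate error, because even a normal reference gives only 96.1% at 104 per school.

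This should be fixed before analysis: the omission is certain, and the rate depends on choices the SAP leaves open.

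**What to change.** In the SAP's Data analysis section, state that for the intervention-versus-control contrast on linear outcomes, standard errors are clustered on school with a bias-reduced (CR2) estimator, and that tests and intervals use a t reference with Satterthwaite df. An equivalent small-sample method would also serve. So would a within-block permutation test over the 6 × 6 × 6 = 216 allocations, whose attainable two-sided level is 10/216 = 4.6%. For non-linear outcomes, require a suitable small-sample method without presuming it is CR2.

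Under Primary effectiveness aim, say whether block-by-time terms are in the primary model. In the Power section, state whether the test is two-sided and restate power on the matching df and contrast. For a 7-month comparison this is about 77% (10 df) or 75% (8 df) with 49 retained per school, and 92% or 90% with 104.

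The cost is wording, plus intervals 1.06-1.25 times as wide as the ordinary options on 10 df, or 1.23-1.44 times on 8 df. Design and data collection do not change.

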#### ***Primary effectiveness aim***

Multi-level mixed effect models will be used to control errors of non-independence and heteroscedasticity caused by individual, class and school heterogeneity, and potential covariates identified a priori based on the literature and theory that are relevant to SSB behavior changes. The treatment effect models used in this study will contain outcomes of interest as dependent variables (e.g., SSB kcal, quality of life measures etc.). Specific mixed effect link function will be chosen to fit different outcome distributions. The models will control those unobserved effects that are fixed over time at three different levels (i.e., individual student, class, and school) and

those unobserved time and block fixed effects that are individual-class-school-invariant. To further examine intervention treatment effect differences across blocks, we will modify the models to allow group indicator to interact with time-block fixed effects.

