- Primary effectiveness aim: assess changes in SSB behaviors at 7-months (immediately post program) among students receiving Kids SIPsmartER, as compared to control schools. Secondary aims:
- Secondary effectiveness & maintenance outcomes: determine changes in secondary student outcomes (e.g. quality of life,

BMI z-score, theory-related variables, health and media literacy); changes in caregiver SSB behaviors and home environment; and maintenance of outcomes at 19-months post-baseline.

- Reach: assess the reach and representativeness of Kids SIPsmartER, among students and parents/guardians.
- Implementation, adoption, and school-level maintenance: using a mixed-methods approach with interviews, surveys, observation, and process evaluation strategies, assess the degree to which teachers implement Kids SIPsmartER as intended and the potential for institutionalization within the schools.

If found to be effective among students, and if implementation at the school level shows strong potential, our mid-term goal is scale up Kids SIPsmartER to reach additional middle schools. The long-term goal of this line of health promotion and prevention research is to sustain multi-level strategies to reduce SSB-related health inequities and chronic conditions (e.g. obesity, cancer, diabetes, dental decay) in rural Appalachia.

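### The SAP does not say how baseline SSB intake enters the primary model; its wording points to a difference-in-change contrast, where baseline adjustment would generally be more precise

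*SAP*

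**What the plan says.** The SAP (Primary effectiveness aim) specifies multi-level mixed effect models with covariates to be chosen beforehand from literature and theory, none of which it lists. It continues: "The models will control those unobserved effects that are fixed over time at three different levels (i.e., individual student, class, and school"), together with "those unobserved time and block fixed effects that are individual-class-school-invariant". The next SAP section says that the time indicator will be changed to read effectiveness at 3, 7 and 19 months.

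The Protocol (Study Overview) words the primary aim as to "assess changes in SSB behaviors at 7-months (immediately post program) among students receiving Kids SIPsmartER, as compared to control schools".

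The Protocol (Data Sources, Student Assessment Packet) has SSB intake measured at baseline and at 3, 7 and 19 months in control and intervention schools alike. Study Logistics randomises four schools, two per arm, in each of three blocks.

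The power section rests on a "small 7-month effect size of 0.3, a 0.05 type I error, and a 0.01 ICC". It contains no baseline-to-follow-up correlation.

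**The concern.** Removing everything that is constant over time for a student, and reading the effect through a time indicator, gives the arm difference in change if baseline means are left free by arm. With complete data at two time points this is so whether the student effects are fixed or random. A change contrast fixes the coefficient on baseline at 1. Randomisation gives the arms the same expected baseline, so that coefficient can be estimated, or the baseline means held common, usually with a smaller standard error and with no new data.

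No sentence in the SAP names baseline SSB intake as a covariate or sets a common baseline mean. The choice is therefore left open for the primary estimate, and the wording leans to the less precise option. There are only six schools per arm, and the SAP regards its 54-student minimum as adequate, so the precision lost could matter in the smaller scenario.

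**Working it through.** **Inputs from the SAP power section:** standardised effect 0.3, type I error 0.05 (two-sided assumed), ICC 0.01, six schools per arm, and 49 or 104 students retained per school. **Assumed, because the documents do not give them:** the student-level correlation rho between baseline and 7 months, the correlation rs of school effects over time, and equal SD (set to 1) at both times.

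**The SAP's own figure.** The SAP states that "a total of 12 schools/clusters (6 schools per condition) are needed, with 54 enrolled students per school" for 80% power. For a 7-month comparison ignoring baseline, the variance of a school mean at m = 49 is 0.01 + 0.99/49 = 0.0302. The SE of the arm difference is √(0.0302 × 2/6) = 0.100. Power is 76.9% (t, 10 df) or 84.9% (normal approximation). At m = 104 it is 91.7% or 96.1%. The stated 80% is met approximately only if all 54 enrolled students are analysed on 10 df (79.4%). The stated 99.99% (also given as 99.9%) is not reproduced. That mismatch is a separate matter; these values serve here only as the reference.

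**Student-level variance, relative to ignoring baseline:**
- change: 2(1 − rho)
- baseline-adjusted: 1 − rho²
- adjusted over change: (1 + rho)/2, which is 0.65, 0.70, 0.75, 0.80 and 0.85 at rho 0.3, 0.4, 0.5, 0.6 and 0.7

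The change factor is 1.2 at rho 0.4 and 1.0 at rho 0.5. Below 0.5, a change analysis has more variance than one that ignores baseline.

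**School-mean variance, with rs = rho:**
- change: 2·ICC·(1 − rs) + 2(1 − ICC)(1 − rho)/m
- adjusted: ICC·(1 − rs²) + (1 − ICC)(1 − rho²)/m

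Worked example, rho 0.4 and m = 49:
- change: 0.0120 + 0.0242 = 0.0362; SE √(0.0362 × 2/6) = 0.110; 0.3/0.110 = 2.73; power 69% (10 df)
- adjusted: 0.0084 + 0.0170 = 0.0254; SE 0.092; 0.3/0.092 = 3.26; power 83% (9 df)

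| Retained per school | rho | Change (10 df) | Adjusted (9 df) |
|---|---|---|---|
| 49 | 0.4 | 69% | 83% |
| 49 | 0.5 | 77% | 87% |
| 49 | 0.6 | 85% | 91% |
| 104 | 0.4 | 86% | 95% |
| 104 | 0.5 | 92% | 97% |
| 104 | 0.6 | 96% | 98% |

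**Simulation.** With 12 schools, ICC 0.01, rho 0.4 to 0.7, rs 0 to 0.8 and 4,000 runs per setting, the adjusted/change variance ratio was 0.64 to 0.87 at 49 per school and 0.62 to 0.88 at 104. Both estimators were unbiased.

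**Where the gain fails.** With one student-level slope b = rho and no school-mean term, the school part of the adjusted variance is ICC·(1 − 2b·rs + b²). Take rho 0.4, m = 104 and rs 0.95:
- ICC 0.01: adjusted 0.0040 + 0.0080 = 0.0120; change 0.0010 + 0.0114 = 0.0124; ratio 0.97
- ICC 0.02: adjusted 0.0080 + 0.0079 = 0.0159; change 0.0020 + 0.0113 = 0.0133; ratio about 1.2, so change is the more precise

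At ICC 0.01 and 49 retained, the same rs gives about 0.83.

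**The case against.** The strongest reply is that the SAP never commits to a change-score analysis. It gives no treatment-effect parameter, calls the model mixed, cites a random-effects source and allows unnamed prior covariates, of which baseline SSB intake is an obvious candidate. Students also have a 3-month SSB measurement, so repeated outcome rows do not prove that baseline is one of them. A reader might infer that the plan forces the baseline coefficient to 1 and so loses 15% to 35% of its precision. The text does not support that; it supports only that the matter is unstated and the wording leans that way.

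A reader might also infer that a change contrast has no merit. That is not supported either. Consent forms, principal letters and flyers differ by arm (Protocol, Recruitment & Consent), so consent follows allocation and the consenting samples could differ at baseline. The SAP itself makes individual-level selection a focus. This is a sound reason to report difference-in-differences, though less so to leave the primary estimator open.

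Three further points stand:
- It is not true that adjustment always beats change; the last calculation shows a reversal.
- The SAP does not say whether the 0.3 and the 0.01 refer to 7-month values or to changes. If to changes, the shortfall against the SAP's own power basis disappears.
- The Protocol expects about 114 participating students per school, so the 49-retained figures describe the minimum, not the expected case.

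The time and block effects can reasonably be read as block-specific time effects, so no omission of block is claimed.

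**Conclusion.** The point holds as a gap in specification with a likely cost in precision, not as a demonstrated wrong analysis. The primary model should say how baseline SSB intake is used.

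If the model is run as the wording suggests, with free baseline means, the adjusted alternative has 0.65 to 0.85 of its student-level variance for rho 0.3 to 0.7. At rho 0.4 to 0.5 that is 10 to 14 points of power at 49 retained per school. At 104 retained and rho 0.5 it is about 5 points. These sizes rest on an assumed rho, on school-level correlation equal to rho, on ICC 0.01 and on equal SDs. The direction is dependable unless school means are very stable over time and a single student-level slope is used. Neither estimator is invalid under randomisation with comparable consent.

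**What to change.** Write out the primary model and define the primary estimate as the arm difference in 7-month SSB intake, from one of:
- a longitudinal mixed model with one common baseline mean for both arms within block, block-specific time effects, and school, class and student random effects including school-by-time; or
- the 7-month value adjusted for the student's baseline SSB intake, the school-mean baseline SSB intake and block, with school and class random effects.

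The school-mean term, or the school-level structure of the longitudinal model, deals with the case in which a single slope loses to change. Report the difference-in-differences estimate as a sensitivity analysis, because consent follows allocation.

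The cost is a short SAP amendment and no new data. The two estimates can diverge if the consenting samples differ by arm at baseline, and the SAP should say how that would be interpreted. The covariate-adjusted version drops students without a baseline value unless missing baselines are handled explicitly. The Protocol's Study Overview places completion of the 7-month primary outcome by May 2021, so the amendment should be dated and should state whether outcomes by arm had already been examined.

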**Study Logistics** This study began in the 2018-19 school year and will run for 7 years. All human subjects will come from 12 middle schools. To be eligible for the study, schools should be in the geographical Central Appalachia catchment area in southwest Virginia, have approximately 80 to 200 students in the 7th grade, and have an 8th grade within the same school building. The latter eligibility criteria is in effort to promote student retention at the 19-month data point. We have identified at least 22 schools that meet this criteria. If more schools are needed, we can also extend our catchment area in Central Appalachia, including to qualified schools in West Virginia.

A key intent of our design is to allow schools equal opportunity to benefit, regardless of randomized treatment allocation. For pragmatic reasons, we are not proposing a simple randomization approach in which all 12 schools (clusters) are randomized at the out-set of the study. Due to turnover in administration/teachers and fluctuations in resources, our school informants indicated it is unrealistic for a school to enter into an agreement for a research project that is as far as 3-4 years out. Therefore, to promote sound randomization and school retention, we propose to recruit and randomize 4 schools [2 Intervention Schools (IntS) and 2 Control Schools (ConS)] in 3 separate blocks. Among Intervention Schools (IntS), both students and parents complete the evaluation components and receive Kids SIPsmartER. In Control Schools (ConS), both students and parents only complete the evaluation components, they do not receive the Kids SIPsmartER program. Control schools become Delayed Intervention Schools (DIntS) schools in the following academic year and receive the Kids SIPsmartER program (See Attachment in Study Overview file).

[MODIFICATION August 10 2021]: Throughout the execution of in-person study activities, researchers will abide by current UVA policy regarding masks as well as any school-level policies that exceed UVA policy.

Within each block of our stepped wedge design, we will use pure randomization. IntS and Delayed Intervention Schools (DIntS) are co-delivered by researchers and 7th grade teachers, whereas Support Schools (SupS) and Organizational Maintenance (OrgM) School are delivered by 7th grade teachers. Student and caregiver individual-level data is collected during IntS, DIntS, ConS and

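### The block-by-group analysis compares two schools with two in each block; with uncorrected robust standard errors a test of it far exceeds its nominal 5% error, and a valid test has little power

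*SAP*

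**What the plan says.** The Protocol (Study Overview, Study Logistics) explains why schools are not all randomized at the outset: "we propose to recruit and randomize 4 schools [2 Intervention Schools (IntS) and 2 Control Schools (ConS)] in 3 separate blocks". The SAP (Power calculation and sample size) confirms the total: "a total of 12 schools/clusters (6 schools per condition) are needed".

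Under Primary effectiveness aim, after describing the multilevel model with time and block effects, the SAP adds: "To further examine intervention treatment effect differences across blocks, we will modify the models to allow group indicator to interact with time-block fixed effects". Under Data analysis it sets a general rule: "All analysis will use cluster-robust standard error adjustment".

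Neither document gives a small-sample correction, a reference distribution, degrees of freedom, a clustering level or a significance level for the block comparison. Neither calls it descriptive or exploratory, though the SAP's wording leans that way.

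**The concern.** Once group interacts with block, the effect in a block is the difference between two school means and two others. The uncorrected sandwich variance is built from residuals around those two-school means. Such residuals are too small, and very few of them are independent. Recruiting more students per school does not help, because the shortage is of schools.

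At stake is a reported finding that the programme worked in some blocks and not in others, produced by the variance estimator and not by the data. The reverse error is also possible: a non-significant result from a valid test could be taken as evidence of consistency, although the design cannot show that.

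**Working it through.** **Inputs.** Three blocks of 2 v 2 schools (Protocol, Study Logistics). For planning, the SAP assumes "a small 7-month effect size of 0.3, a 0.05 type I error, and a 0.01 ICC", with 49 or 104 students retained per school. Assumed here because the documents are silent: two-sided test, clustering by school, equal school sizes, only the first-year intervention and control schools, and variance at a single time point. The SAP states no error rate or power for the block comparison, so there is no figure of its own to reproduce. Its 80% and 99.99% refer to the overall effect and are not used here.

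**School-mean variance in SD units.** v = 0.01 + 0.99/m.
- m = 49: v = 0.0302
- m = 104: v = 0.0195

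A block effect has true variance v/2 + v/2 = v, so its SE is 0.174 (m = 49) or 0.140 (m = 104).

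**Bias of the uncorrected robust variance (CR0).** In a two-school cell each school has leverage 1/2. The squared residuals sum to (y1 - y2)²/2, with expectation v. Dividing by 2² gives v/4 per cell, against a true v/2. CR0 is therefore half the true variance on average. CR1 multiplies CR0 by 12/11. CR2 (bias-reduced) doubles CR0 here and so removes the bias.

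**One pre-chosen contrast of two blocks.** It uses four cells with one df each. The CR0 statistic is distributed as √2 × t(4), and v cancels. Rejection rates under no true difference:
- CR0, z: P(|t4| > 1.96/√2) = 23.8%
- CR1, z: 22.1%
- CR0, t(11): 19.5%
- CR1, t(11): 17.9%
- CR2, t(8): 8.2%
- CR2, t(4): 5.0%

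**Joint test that all three block effects are equal (2 df).** Simulated with 100,000 null trials per scenario, equal sizes:

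| Variance | chi-square | F(2,11) | F(2,8) | contrast-specific df |
|---|---|---|---|---|
| CR0 | 38% | 30% | 27% | - |
| CR1 | 35% | 27% | 24% | - |
| CR2 | 20% | 14% | 12% | 3.4% (HTZ) |
| School-level, pooled variance | - | - | - | 4.9% (F(2,6)) |

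CR2 with 8 df gives 5.0% for the main effect with block terms, so the 12% and 8% above show what happens when those df are carried over to the interaction.

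**Sensitivity.**
- The rates hardly change with the ICC or with students per school when sizes are equal.
- With unequal sizes, uncorrected rates reach about 44% (joint) and 28% (one contrast). The contrast-specific methods stay within about 3-7%.
- In 1,500 student-level simulations with class and school effects and unequal sizes, analysed by least squares with school-clustered SEs, the joint test rejected in 37.0% (chi-square) and 26.9% (F), and one contrast in 24.3% (z) and 19.3% (t(11)).
- Clustering on class in that check still gave 23.5% (joint) and 17.5% (one contrast).

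**Power of the valid F(2,6) test.** Let δ be the spread between best and worst block, with the third midway. The noncentrality is δ²/(2v). For δ = 0.3 it is 0.09/0.0604 = 1.49 (m = 49) and 0.09/0.0390 = 2.31 (m = 104), which gives power of 13% and 17%. Power of 80% needs δ of about 1.0 SD (m = 49) or 0.80 SD (m = 104).

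**Chance spread under one common effect.** The best-minus-worst range of the three estimates exceeds 0.3 SD in 44% (m = 49) or 28% (m = 104) of trials. For a given pair of blocks the figures are 22% and 13%.

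**The case against.** The strongest reply is that the SAP specifies no test. It says only that it will look further at block differences, sets no alpha or decision rule, and claims power only for the primary 7-month outcome. Low power for an exploratory interaction is not an error in itself. This stands, and it lowers the priority. It does not justify the standard errors: the SAP applies robust SEs to all analyses, so any p-value or interval from the interaction would inherit the error rates above.

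A second reply is that the root defect is the missing small-sample correction under Data analysis, which also affects the primary test. That is largely right. A single rule requiring CR2 with df computed for each contrast would cover both. A rule with df fixed for the main effect would not.

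Three stronger readings are tempting, and the documents or the arithmetic do not support them:
- *The design cannot support any robust test of block differences.* It can: CR2 with 4 df holds 5.0% for one contrast, and HTZ is slightly conservative for the joint test. What the design lacks is information.
- *A false block result would be a false claim about COVID closures.* The Protocol describes changes in delivery and survey mode, but the text does not tie blocks to school years or plan that interpretation.
- *The pooled F(2,6) analysis is valid without conditions.* It assumes equal school variance across blocks. If one block's variance is twice the others', its nominal 95% pooled interval covers about 90%; at four times, about 85%. The F test itself stays at 5-7%.

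**Conclusion.** The concern holds as a lower-priority point. As written, the block comparison combines 2 v 2 schools per block with robust standard errors that have no stated correction, so its false-positive rate is roughly four to eight times nominal. That rests on school-level clustering, a two-sided 5% level and equal sizes. It was derived from school means and least squares; the SAP's mixed model itself was not fitted. The error rate can be repaired by a contrast-specific method, but the lack of power cannot be. A significant result from the uncorrected analysis would be weak evidence of a difference, and a non-significant result from a valid one would not show consistency. The power and chance-spread figures also depend on single-time-point variance and would improve if baseline adjustment removes variance.

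**What to change.** Add to the SAP, under Primary effectiveness aim:

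> The block analysis is exploratory. Block-specific effects will be reported with confidence intervals. Any p-value for block differences will use a small-sample method with degrees of freedom specific to that contrast (CR2 with Satterthwaite or HTZ df, or a school-level F test with 6 residual df, which assumes equal school variance across blocks). No claim that effects differ or are consistent across blocks will rest on it.

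The CR2 option keeps the SAP's individual-level analysis; the school-level F test departs from it for this one comparison.

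The cost is a few sentences and one short analysis. The downside is wide block intervals. With pooled variance and t(6) = 2.447, the half-width is 2.447 × 0.140 = 0.34 SD at 104 retained and 2.447 × 0.174 = 0.43 SD at 49. Baseline adjustment could narrow them. For example, if the baseline to 7-month correlation were 0.7 at both student and school level (an assumption), analysing changes would multiply the half-width by √(2 × 0.3) = 0.77, so 0.34 would become about 0.26.
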